Subjects will begin their meditation practice at home using suggested guided meditations. Subjects will be asked to create an account on the meditation website InsightTimer. This website has an accompanying smart device application that allows users to access guided meditations and timed sessions. With an account, users' session data is logged. Subjects will be encouraged to use guided meditations of their choice or timed meditation using the InsightTimer. They will be asked to practice a half hour, five days per week for eight weeks. Subjects must complete at least one hour per week to remain in the study. Every week during the study, subjects will be asked to submit their data from the application into REDCap. Subjects will have the PI's email and a phone number for technical assistance.

Subjects' meditation practice will last for eight weeks with measures being utilized after week three and week eight. The following measures will be sent to participants by email and submitted through REDCap.

- Tinnitus Handicap Questionnaire
- Tinnitus Handicap Inventory
- Tinnitus Functional Index
- Hospital Anxiety and Depression Scale
- Mindful Attention Awareness Scale

← **Commented [RJ25]:** What technology is needed?

**Commented [RJ26]:** What application? Please describe the requirement here in further detail.

**Commented [BF27R26]:** I hope this is clearer now.

← **Formatted:** Bulleted + Level: 1 + Aligned at: 0.75" + Indent at: 1"

**Commented [RJ28]:** You describe above participation for 3 weeks. Are there additional research procedures or activities that are required up to 8 weeks?

**Commented [BF29R28]:** My language was unclear. The intervention lasts 8 weeks with measures after weeks 3 and 8.

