## 20.0      Withdrawal of Subjects

**N/A:** This study is not enrolling subjects. This section does not apply.

Commented [RJ48]: Please respond to this section.

20.1 *Describe anticipated circumstances under which subjects may be withdrawn from the research without their consent.*

Response: Subjects may be withdrawn for the following reasons:

- Failure to submit mediation data in a timely manner.
- Failure to complete surveys and questionnaires in a timely manner.
- Failure to comply to participating in the intervention. Subjects practicing meditation less than one hour per week may be withdrawn from the study.

20.2 *Describe any procedures for orderly termination.*

*NOTE: Examples may include return of study drug, exit interview with clinician. Include whether additional follow up is recommended for safety reasons for physical or emotional health.*

Response: Participants will be informed of their removal from the study and asked to complete questionnaires (Tinnitus Handicap Questionnaire, Tinnitus Handicap Inventory, Tinnitus Functional Index, Hospital Anxiety and Depression Scale, Mindful Attention Awareness Scale) via the REDCap system. This intervention poses low risk from discontinuing abruptly.

20.3 *Describe procedures that will be followed when subjects withdraw from the research, including retention of already collected data, and partial withdrawal from procedures with continued data collection, as applicable.*

Response: Data already collected from subjects who withdraw will be analyzed up to the point of their last completed questionnaires.

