## 21.0 Risks to Subjects

21.1 *List the reasonably foreseeable risks, discomforts, hazards, or inconveniences to the subjects related to their participation in the research. Consider physical, psychological, social, legal, and economic risks. Include a description of the probability, magnitude, duration, and reversibility of the risks.*

*NOTE: Breach of confidentiality is always a risk for identifiable subject data.*

Commented [RJ49]: Please respond to this section.

Response: Subjects will be asked to be seated and still for long periods of time. Some subjects may experience minor physical discomfort. There may also be an increased risk for circulation to be reduced due to subjects being in one position for an extended period of time.

21.2 *Describe procedures performed to lessen the probability or magnitude of risks, including procedures being performed to monitor subjects for safety.*

Response: To reduce discomfort and poor circulation that can occur in seated meditation, subjects will also be instructed to participate in lying or walking meditation.

21.3 *If applicable, indicate which procedures may have risks to the subjects that are currently unforeseeable.*

Response: N/A

21.4 *If applicable, indicate which research procedures may have risks to an embryo or fetus should the subject be or become pregnant.*

Response: N/A

21.5 *If applicable, describe risks to others who are not subjects.*

Response: N/A

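### Exit questionnaires are specified only for removed subjects, late forms alone can bring removal, and no reason for stopping is recorded, so outcomes of voluntary leavers and worsening as a cause of leaving can be lost

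*Protocol*

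**What the plan says.** **Schedule.** Section 10.1 states that "meditation practice will last for eight weeks with measures being utilized after week three and week eight". Section 10.2 adds a baseline set before week 1 and a weekly REDCap entry of meditation time.

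**Removal.** Section 20.1 lists three grounds on which a subject may be removed without agreement:
- "Failure to submit mediation data in a timely manner"
- "Failure to complete surveys and questionnaires in a timely manner"
- too little practice: "Subjects practicing meditation less than one hour per week may be withdrawn from the study"

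Section 10.1 puts the practice rule more firmly: "Subjects must complete at least one hour per week to remain in the study".

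**Exit assessment.** Section 20.2 says: "Participants will be informed of their removal from the study and asked to complete questionnaires". The set is the same five instruments used at weeks 3 and 8 (THQ, THI, TFI, HADS, MAAS).

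**Withdrawal.** Section 20.3 says: "Data already collected from subjects who withdraw will be analyzed up to the point of their last completed questionnaires". Its template prompt raises continued data collection after partial withdrawal; the response provides none.

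**Reasons and harms.** No section collects a reason for stopping. Items 19.1 to 19.9, on safety data, are all answered as not applicable. Section 21.1 nevertheless accepts that "Some subjects may experience minor physical discomfort".

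**The concern.** Whom to follow after exit, and what to ask them, are data-collection rules. They cannot be left to the analysis, because outcomes that were never requested cannot be recovered later.

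The study has one arm (Section 4.1), so there is no comparison group in which similar attrition could be seen. If subjects whose tinnitus, mood or comfort worsens are more likely to stop or to fall behind on forms, those who remain are a favourably selected group and the before-after change looks better than it was. Early leavers also matter for the hypothesis in Section 1.2, which relates reduction in bother to time spent meditating: they are among those with the fewest total minutes.

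The late-form grounds add a second route to missing outcomes, this one created by the protocol. A subject who is still practising can lose the week-8 assessment because an earlier form came in late.

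**Working it through.** The protocol states no figure on this point: Section 17.2 answers the power analysis as not applicable, and no dropout rate, effect size or standard deviation is given. The check is therefore a reading of the sections side by side, followed by an illustration on assumed values.

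**1. What each kind of leaver would leave behind, following the text as written**

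| How the subject leaves | Outcomes held | Exit set requested? | Reason recorded? |
|---|---|---|---|
| Announces withdrawal before week 3 | Baseline only | No (20.3) | No |
| Announces withdrawal between weeks 3 and 8 | Baseline, week 3 | No (20.3) | No |
| Goes silent and is removed | Sets completed so far | Yes (20.2) | Administrative ground at most |
| Goes silent and is not removed | Sets completed so far | No | No |
| Still practising, removed for late forms | Sets completed so far | Yes, at removal; week 8 can be lost | Administrative ground at most |

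Row 1 gives no change score, so the subject cannot enter the paired t-test that Section 17.1 names as a possibility, nor a correlation of change with minutes. Row 2 gives a week-3 change but nothing at exit or at the end of the eight weeks. In row 5 the exit set is taken at removal and does not stand in for the scheduled week-8 measure.

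**2. Which row a low-practice subject falls in.** Section 10.1 words the one-hour rule as a condition of staying in; Section 20.1 makes removal discretionary. Under the first, every subject below the threshold is removed and sent the exit set. Under the second, some are not. The two sections therefore give different answers to who receives the questionnaires.

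**3. Illustration of size.** From the protocol: target enrolment 30 (Section 5.1). Assumed: completers change by -10 points on some scale; a share of 10% (3 subjects) or 20% (6 subjects) leaves before week 3 and supplies no exit data; the leavers' true change is 0 or +5.

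All-enrolled mean = (completers × -10 + leavers × leavers' change) / 30. Overstatement = 10 divided by the size of that mean, minus 1.

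- 10% leave, change 0: (27 × -10 + 3 × 0)/30 = -9; 10/9 = 1.11, overstatement 11%.
- 10% leave, change +5: (27 × -10 + 3 × 5)/30 = -8.5; 10/8.5 = 1.18, overstatement 18%.
- 20% leave, change 0: (24 × -10 + 6 × 0)/30 = -8; 10/8 = 1.25, overstatement 25%.
- 20% leave, change +5: (24 × -10 + 6 × 5)/30 = -7; 10/7 = 1.43, overstatement 43%.

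The absolute bias is the share leaving times the gap between completers and leavers: at 20% and a gap of 15 points, 0.20 × 15 = 3 points, which is the difference between -10 and -7.

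**The case against.** Several stronger readings are tempting, and the protocol does not support them.

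- **A reader might infer that subjects who stop on their own leave no outcome at all.** They do not: Section 20.3 keeps what was collected, and anyone leaving after the week-3 set has a computable change on every repeated scale. Only leavers before week 3 have no post-baseline outcome.
- **A reader might infer that silent stoppers escape assessment.** Weekly entries would reveal the silence, the Section 20.1 grounds would apply, and removal brings the exit set. The gap is the subject who announces withdrawal, plus silent subjects whom the investigator does not remove.
- **A reader might take the three grounds in Section 20.1 as a list of reasons for leaving, so that voluntary exits are miscoded as poor compliance.** That item concerns removal without the subject's agreement. Discomfort would not belong there, and its absence proves nothing about coding.
- **A reader might infer that the data could never show harm.** Three tinnitus scales and the HADS are repeated and can show worsening in those who answer them. What is not captured is worsening as the cause of stopping.

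It is also fair to say that removal for lateness is discretionary and that nothing forbids a reminder. The inputs to the illustration come from outside the protocol, and it treats only a mean change, whereas the stated hypothesis is a correlation. Handling of missing data in the analysis may sit in a statistical analysis plan that is not shown.

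All of this limits the point without removing it. Sections 20.2 and 20.3 still request no exit outcome from voluntary leavers, no reason is recorded for anyone, and lateness alone may still end follow-up. An analysis plan cannot mend any of these.

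**Conclusion.** The concern holds in a limited form. Followed as written, the protocol loses the post-baseline outcome of voluntary leavers before week 3 and the exit and week-8 outcomes of later ones. It also permits late paperwork to end the week-8 assessment of a practising subject, and it records no reason for stopping from anyone, removed or not.

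The direction of bias depends on an assumption that is plausible but untested here: that subjects who feel worse stop or fall behind more often. The size cannot be derived from the protocol. The 11-43% range holds only if 10-20% leave before week 3, none of them supplies exit data, and their changes lie between 0 and +5 against -10 in completers. If fewer leave, if some provide exit data, or if their outcomes resemble those of completers, the overstatement is smaller or absent.

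This should be corrected before enrolment, because it is cheap to do then and cannot be repaired afterwards.

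**What to change.** 1. In Sections 20.2 and 20.3, ask every subject who stops, whether removed or by own choice, to complete the existing REDCap set at exit and again at that subject's scheduled week-8 date, unless consent to follow-up is withdrawn.
2. Add one REDCap item for the main reason for stopping, for example discomfort, tinnitus worse, mood worse, lack of time, technical problems or other.
3. In Section 20.1, state that lateness of meditation entries or questionnaires alone does not end outcome follow-up, and that after a reminder late forms are accepted with their actual completion date.
4. Reconcile the wording of the one-hour rule in Section 10.1 with that in Section 20.1, since this decides who is sent the exit set. Which version should stand is for the investigator to settle.

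The cost is some protocol and consent wording, one item and reminders; the instruments and the REDCap system are already in place. The downsides are some off-schedule questionnaires to date and handle in the analysis, and a small added burden on leavers and on an unfunded investigator who runs all aspects of the study in 6 to 12 hours a week (Sections 14.2 and 14.4).

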## 1.0 Objectives

1.1 Describe the purpose, specific aims, or objectives of this research.

Response: The purpose of this mixed methods correlational study is to investigate the effects of meditation on the level of bother in tinnitus patients in the United States. The researchers seek to understand the changes in bother as compared to the amount of time spent meditating. Data is obtained through the Insight Timer mediation application. Outcome measures will include several validated and reliable measures.

1.2 State the hypotheses to be tested, if applicable.

NOTE: A hypothesis is a specific, testable prediction about what you expect to happen in your study that corresponds with your above listed objectives.

Response: The reduction level of bother of tinnitus will correlate to the amount of time spent meditating.

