## 10.2 Describe what data will be collected.

*NOTE: For studies with multiple data collection points or long-term follow up, consider the addition of a schedule or table in your response.*

Response:

- [Each week, participants will enter the amount of time spent meditating on a form through REDCap.](#)
- [Before week 1:](#)
  - [Tinnitus Handicap Questionnaire](#)
  - [Tinnitus Handicap Inventory](#)
  - [Tinnitus Functional Index](#)
  - [Hospital Anxiety and Depression Scale](#)
  - [Mindful Attention Awareness Scale](#)
  - [University at Buffalo Tinnitus Intake Questionnaire](#)
- [After week 3:](#)
  - [Tinnitus Handicap Questionnaire](#)
  - [Tinnitus Handicap Inventory](#)
  - [Tinnitus Functional Index](#)
  - [Hospital Anxiety and Depression Scale](#)
  - [Mindful Attention Awareness Scale](#)
- [After week 8:](#)
  - [Tinnitus Handicap Questionnaire](#)
  - [Tinnitus Handicap Inventory](#)
  - [Tinnitus Functional Index](#)
  - [Hospital Anxiety and Depression Scale](#)
  - [Mindful Attention Awareness Scale](#)

 10.3 List any instruments or measurement tools used to collect data (e.g. questionnaire, interview guide, validated instrument, data collection form).

*Include copies of these documents with your submission.*

Response:

- [Tinnitus Handicap Questionnaire](#)
- [Tinnitus Handicap Inventory](#)
- [Tinnitus Functional Index](#)

- Hospital Anxiety and Depression Scale
- Mindful Attention Awareness Scale
- University at Buffalo Tinnitus Intake Questionnaire

**Commented [BF30]:** [https://drive.google.com/open?id=104a3hbqsAAkvfesLVLFQCv168M2\\_RYQa](https://drive.google.com/open?id=104a3hbqsAAkvfesLVLFQCv168M2_RYQa)

10.4 *Describe any source records that will be used to collect data about subjects (e.g. school records, electronic medical records).*

Response: No additional records will be requested or gathered from subjects.

10.5 *Indicate whether or not **individual** subject results, such as results of investigational diagnostic tests, genetic tests, or incidental findings will be shared with subjects or others (e.g., the subject's primary care physician) and if so, describe how these will be shared.*

Response: Individual subject results will not be shared with any other parties.

10.6 *Indicate whether or not **study** results will be shared with subjects or others, and if so, describe how these will be shared.*

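### Subjects removed for not submitting meditation data are asked at exit for five scales but not for the outstanding minutes, so the exit outcome can cover a longer period than the recorded exposure

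*Protocol*

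**What the plan says.** **Hypothesis (Protocol 1.2).** "The reduction level of bother of tinnitus will correlate to the amount of time spent meditating".

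**How minutes reach the study (10.1, 10.2).** The only route described is the subject's own weekly entry. In 10.1: "Every week during the study, subjects will be asked to submit their data from the application into REDCap". In 10.2, each week, "participants will enter the amount of time spent meditating on a form through REDCap". Section 10.4 provides for no further records.

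**Where the minutes also exist (10.1).** "With an account, users' session data is logged". The log sits in the subject's account, and the protocol describes no direct study access to it.

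**Removal (20.1).** The first listed ground is "Failure to submit mediation data in a timely manner" (the third word is evidently a slip for meditation). Removal is at the team's discretion.

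**Exit request (20.2).** Removed subjects are told of their removal and "asked to complete questionnaires (Tinnitus Handicap Questionnaire, Tinnitus Handicap Inventory, Tinnitus Functional Index, Hospital Anxiety and Depression Scale, Mindful Attention Awareness Scale"), through REDCap. Meditation time is not listed.

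**Use of the data (20.3).** "Data already collected from subjects who withdraw will be analyzed up to the point of their last completed questionnaires".

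**The concern.** The hypothesis needs two quantities per subject over the same period: minutes practised and change in bother. For subjects removed under the first ground in 20.1, the exit procedure updates the second and not the first. The weeks without minutes are the weeks that led to removal, and 20.3 lets the exit scales stand as the last outcome.

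At stake is whether the exit outcome of these subjects can be used for 1.2 without an assumption about the unreported weeks. This concerns what is collected. An analysis plan can say how to handle a gap, but it cannot recover a figure nobody asked for.

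**Working it through.** The protocol states no figure on this point (17.2 answers the power question as not applicable), so there is none to reproduce. The check sets the sections side by side and then sizes the gap for one subject.

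**Step 1. What is held for a subject removed under the first ground of 20.1**

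| Item | Source | Period covered |
|---|---|---|
| Baseline scales | 10.2 | before week 1 |
| Minutes | 10.1, 10.2, weekly entry | submitted weeks only |
| Week-3 scales | 10.2, if reached and completed | to end of week 3 |
| Exit scales | 20.2, if completed | to day of exit |
| Minutes for unsubmitted weeks | no section asks for them | none |

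The last two rows do not match. The week-3 row does match the minutes for weeks 1-3, if those were submitted.

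**Step 2. Size of the gap for one subject.** Inputs from 10.1: requested practice 30 min × 5 days = 150 min/week; minimum to stay in the study 60 min/week. Assumed for illustration: weeks 1-3 submitted, weeks 4-5 not, removal after week 5, exit set completed, and 150 min/week practised in weeks 1-3.

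- Recorded: 3 × 150 = 450 min.
- Practised by exit, if the request was met throughout: 5 × 150 = 750 min.
- Not recorded: 750 − 450 = 300 min, and 300/750 = 40%.

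The true amount in the two missing weeks is unknown:

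| Practice in weeks 4-5 | Missing minutes | True total by exit |
|---|---|---|
| none | 0 | 450 |
| minimum, 2 × 60 | 120 | 570 |
| as requested, 2 × 150 | 300 | 750 |

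With equal practice each week, one missed week of five leaves 1/5 = 20% unrecorded. If no week was ever submitted, the share is 100%.

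**Step 3. Effect on the study.** The protocol gives no number of removals. With the target of 30 in 5.1, each affected subject is 1/30, about 3% of the sample. Going further needs a removal rate, a distribution of minutes, a true correlation and a rule for missing weeks, and none of these is in the document.

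**The case against.** **The affected group is narrow.** This stands. Subjects removed for practising under an hour a week are normally identified from minutes they did submit. Those removed for late questionnaires may have full minutes. Late submitters may have their minutes on record already. The gap bites only when someone who skipped the weekly form goes on to complete the exit scales.

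**Exposure is not absent.** This also stands. Submitted weeks are kept, and a subject who reached week 3 may have a complete pair to that point. A reader might infer that these subjects contribute nothing to 1.2; the documents do not support that.

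**The gap can be handled in analysis.** Largely true. A reader might infer that such subjects must be either dropped or given zero minutes for the missing weeks. The protocol states no such rule. Averaging the submitted weeks, using the week-3 pair and imputation are all open, and the choice belongs to an analysis plan.

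The choice matters. Take as assumptions 30 subjects, mean 120 min/week (SD 35, floor 60), a true correlation of 0.40, and 6 subjects lacking weeks 4-5 of 5. Scoring those weeks as nil lowers simulated power from about 60% to about 45%. Averaging the submitted weeks costs about one percentage point, if week-to-week SD is 30 and non-submission is unrelated to practice. The larger loss therefore comes from a scoring rule the protocol never adopts and from an assumed 6 removals in 30. If the missed weeks were weeks of less practice, averaging would leave some error.

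**Paired t-tests or ANOVA (17.1) need no minutes.** True for the average change from baseline. It does not help hypothesis 1.2, the only one stated.

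**Section 20.2 is about orderly termination, and late entry is not barred.** Fair. But 20.2 does name what is requested, and an entry that is merely not barred is not an entry that is asked for.

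**Conclusion.** The omission is real and minor. For subjects removed because meditation data were not submitted in time, 20.2 asks for the outcome and not for the outstanding exposure. Where the exit set is completed, that last pair is incomplete for hypothesis 1.2.

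The 40% shortfall in the example rests on two missed weeks of five and on the requested practice having been done. The number of subjects affected is not given and could be nil. The documents therefore support no statement about lost power, a diluted correlation or a spurious one.

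The point is still worth acting on. The minutes normally exist in the app log, the subject is already being asked for five scales, and once the exit contact has passed the protocol provides no other occasion to ask.

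**What to change.** In 20.2, add to the exit request the minutes meditated in each week not yet submitted, read by the subject from their own app session log, up to the day the exit questionnaires are completed. Exposure and exit outcome then cover the same period. This is the same information that 10.1 already asks for weekly, so it adds no new data source, and it leaves the removal grounds in 20.1 unchanged.

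The cost is one REDCap field and one sentence in 20.2. The downside is a little extra work for the subject, and some removed subjects will not reply. How any weeks still unreported are treated can be left to the analysis plan.
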